## **Study Protocol**

Prior to any involvement in the study, a study investigator read the VA-approved consent forms in full to the potential subject. Having been read the consent forms and provided with an explanation of the experimental tasks, the potential subject was provided an opportunity to ask questions. Following this, if they agreed to participate, they signed a consent form. Each prosthesis user subject was assessed using their clinically prescribed prosthesis (i.e., socket, suspension system, pylon, and foot).

Following demographic information data collection, retro-reflective markers were attached to the subject with hypoallergenic adhesive tape to anatomical landmarks as specified in the modified Helen Hayes full-body marker set with additional markers placed on the right and left acromion processes, lateral epicondyle of the humerus, and between the styloid process of the radius and ulna. Position of the markers on the prosthetic limb approximated matched those on the contralateral side. Additionally, surface electrodes for measurement of electromyography (EMG), or muscle activity, were placed and secured over the following muscles: tibialis anterior of the sound limb (or both limbs in case of control subjects), medial gastrocnemius of the sound limb (or both limbs in case of control subjects), rectus femoris of both limbs, medial hamstring of both limbs, and gluteus medius of both limbs.

Subjects were requested to perform three biomechanical tasks (randomized prior to their visit) at the JBVAMC Motion Analysis Research Laboratory:

1. Quiet standing with comfortable stance width and eyes open,
2. Quiet standing with comfortable stance width and blindfolded, and
3. Walking at two self-selected speeds (normal and fast) across a level walkway.

**Walking Data Collection**—During the walking trials, subjects walked at a comfortable, normal, self-selected speed down the center of a 10 meter level walkway. The subjects were requested to walk back and forth along this walkway as many times as necessary to produce 10 clean foot strikes (i.e., each foot within the boundaries of at least one force plate). After walking at their normal speed, subjects were then requested to perform the same walking task while at their self-selected “fast” speed, defined as “a speed as if you were hurrying for a bus.”

**Quiet Standing Data Collection**—During standing trials, subjects stood quietly with a comfortable stance width, as determined during an initial practice trial, with each foot on one adjacent force plate. This allowed recording of the plantar center of pressure (CoP) under both limbs by each force plate. The stance position was marked by tracing the feet on the floor. The subject was asked to replicate this stance position for all subsequent trials. During the eyes open condition, subjects were instructed to focus on a visual target mounted at eye level on the wall 5 meters in front. During the eyes closed standing condition, a blindfold was worn by the subjects to remove all visual cues. For each task,

data were recorded for 30 seconds. Three trials of both the eyes open and closed conditions will be performed.

Self-selected walking speeds and stance width were tested to better reflect real-life conditions and facilitate the subjects' comfort during testing. Subjects were provided with seated rest between the three tasks to successfully carry out all walking and standing trials.

**Prospective fall data collection**—Prospective data on falls were collected monthly over a 12 month period following their second visit using a validated, rigorous 'falls calendar' approach. Subjects were provided with twelve (prepaid postage) postcards that consist of a falls calendar. Subjects were instructed on how to use the postcards following established guidelines and post them to the primary investigator directly at the JBVAMC Motion Analysis Research Laboratory every month following the data collection session. This postcard was mailed with no return address to ensure confidentiality. The identity of each subject was determined by their unique subject code, which was written on the postcards before distribution and known only to the research team. Following receipt of a postcard that reported one or more falls during the month data collection period, the subject was contacted via telephone or email and asked standardized questions regarding the location and activity engaged in preceding the fall, what they felt caused the fall, and if injuries were sustained. Subjects were contacted via post, telephone or email if a postcard is not returned within 7 days after each month period and/or to query unclear entries.

**Data Analysis**—Kinematic data were filtered with a low-pass Butterworth filter with a 6Hz cut-off frequency and smoothed in post-processing software. Raw EMG signals were filtered and processed using custom Matlab software. EMG data were normalized to gait cycle time (initial contact to ipsilateral initial contact). To quantify differences in muscle activity during the gait cycle, the integrated EMG (iEMG) for each muscle was calculated as the integral of the EMG profile over time of four regions: 1) braking phase (0-50% of stance), 2) propulsive phase (50-100% of stance), 3) swing phase, and 4) over the entire gait cycle. The iEMG of each subject was normalized by their average iEMG magnitude over the entire gait cycle. Plantar CoP of each limb in the coronal plane (elliptical area) were derived.

## Statistical Analysis Plan

The main effect of amputation and limb side on kinematic variables will be assessed using a linear mixed model analysis for each walking speed separately. The main effect of amputation and limb side on standing balance variables will be assessed using a linear mixed model analysis for each vision condition separately. The main effect of amputation and walking speed on EMG variables will be assessed using a linear mixed model analysis for each muscle group separately. The total number of falls for each group will be calculated for each group.

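### Prosthesis users and controls are non-randomised groups, and the SAP names no demographic covariate and no matching, so any age or sex difference would enter the amputation effect

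*Combined protocol and SAP*

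**What the plan says.** The Study Protocol section describes two kinds of subject. Prosthesis users are tested in the prosthesis already prescribed to them. Controls appear in the electrode placement, for example "tibialis anterior of the sound limb (or both limbs in case of control subjects". Amputation status therefore exists before the study and is not assigned.

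Two phrases could suggest balance between the groups, but neither concerns the allocation or selection of people:

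- "Subjects were requested to perform three biomechanical tasks (randomized prior to their visit" concerns the tasks.
- "Position of the markers on the prosthetic limb approximated matched those on the contralateral side" concerns marker placement on the two limbs of one person.

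Demographic data are gathered ("Following demographic information data collection"), but no use of them is stated.

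The Statistical Analysis Plan names the effects in three mixed models:

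- Kinematics, by walking speed: "The main effect of amputation and limb side on kinematic variables will be assessed using a linear mixed model analysis".
- Standing balance, by vision condition: "The main effect of amputation and limb side on standing balance variables will be assessed".
- EMG, by muscle group: "The main effect of amputation and walking speed on EMG variables will be assessed".

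It names no age, sex or other demographic term, and it does not say that such terms are excluded.

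**The concern.** Amputation is the between-group effect in all three models. In a non-randomised comparison it carries whatever else differs between the groups and is related to the outcome. Age and sex are obvious candidates in a gait and balance study.

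Using a mixed model does not help here. A subject random effect accounts for correlation between limbs or speeds within a person. It cannot separate amputation from age or sex, because all three vary only between people.

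Limb side and walking speed are in a different position. Each is a contrast within the same person, so a difference in age or sex between the groups does not bias it in this way.

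At stake is the interpretation of the amputation effect. With neither matching nor covariates stated, a reader could not tell it from an age or sex difference, should one exist.

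**Working it through.** The plan gives no sample size, significance level, standard deviation or group demographics, so there is no planned figure to reproduce. Every input below is an assumption, chosen to show a range.

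**Inputs (all assumed).** Age gap between groups 0.4 to 0.8 SD; within-group age-outcome correlation 0.2 to 0.4; 10, 15 or 30 subjects per group; two limbs per subject with between-limb correlation 0.7; two-sided 5% level; true amputation effect zero.

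**Step 1, bias.** With age omitted, bias in outcome SDs = correlation × age gap:

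- low: 0.2 × 0.4 = 0.08
- middle: 0.3 × 0.6 = 0.18
- high: 0.4 × 0.8 = 0.32

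**Step 2, rejection rate.** The variance of a subject's two-limb mean is (1 + 0.7)/2 = 0.85. The noncentrality of the two-sample t test is bias / √0.85 / √(2/n). For example:

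- n = 10, high: 0.32/0.922 = 0.347, and 0.347/0.447 = 0.78
- n = 30, high: 0.347/0.258 = 1.34

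The noncentral t distribution with 2n − 2 degrees of freedom then gives:

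| Per group | Low | Middle | High |
|---|---|---|---|
| 10 | 5.4% | 7.0% | 11.4% |
| 15 | 5.6% | 8.1% | 15.1% |
| 30 | 6.3% | 11.5% | 26.2% |

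With one value per subject in place of two limbs, the range is 5.3% to 10.4% at 10 per group and 6.1% to 23.0% at 30. In balanced simulated data the mixed-model amputation estimate equalled the subject-mean estimate to four decimals, so the subject-mean calculation stands in for the planned model.

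**Step 3, effect of adjusting.** The two-limb setting was simulated with a linear age effect, and with sex 50:50 and unrelated to the outcome. Adding age and sex brought the bias to within 0.01 SD and rejection to about 5%. This is a result for age only, and it assumes that the age effect is linear. Sex was given no effect, so in these runs it could only add cost.

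**Step 4, cost of adjusting.** The variance column covers all combinations of gap and correlation, not only those in which the two rise together. The other columns give mean squared error (MSE), adjusted divided by unadjusted.

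| Per group | Change in variance | MSE low | MSE middle | MSE high | MSE at gap 0.8, correlation 0.2 |
|---|---|---|---|---|---|
| 10 | about −5% to +29% | 1.09 | 0.94 | 0.69 | 1.12 |
| 15 | about −8% to +21% | 1.01 | 0.83 | 0.54 | 0.99 |
| 30 | about −12% to +16% | 0.92 | 0.65 | 0.35 | 0.80 |

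Variance rises most where age separates the groups but hardly predicts the outcome. It falls where the gap is small and the correlation is high.

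**The case against.** **The SAP is silent; it does not exclude covariates.** This stands. The SAP is one short paragraph listing effects of interest, and it may not be a full model specification. A reader might infer that an unadjusted analysis is prescribed, or that the controls were not matched. The documents support neither. The available text has no eligibility or recruitment section and part of the document was not available, so matching can only be called not stated. The silence still matters, because it leaves the covariates to be chosen after the data are seen.

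**No harm is shown.** This also stands. No group demographics are given, and nothing in the documents relates age or sex to any outcome. A reader might infer that the amputation effect is biased, or that kinematics and balance are more exposed than EMG. Neither can be concluded. The protocol says that "The iEMG of each subject was normalized by their average iEMG magnitude over the entire gait cycle", which rescales overall magnitude within each subject. That is not an adjustment for age or sex, and how far it lowers the exposure is unknown.

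**Adjustment can cost more than it saves.** This is partly true. At 10 per group with a weak age-outcome correlation, mean squared error is about 1.1 times the unadjusted value. At 15 the two are about equal at worst. At 30 adjustment was better in every scenario run. As the sample size is unknown, this supports showing both analyses.

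**The numerical benefit is a best case and covers age only.** This is correct: the fitted model had the same form as the simulated one. The argument for sex is the structural one given under the concern, not a calculation.

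**Conclusion.** The point holds as a conditional one. The groups are non-randomised, no subject matching or demographic covariate is stated, and a subject random effect would not remove an age or sex difference from the amputation effect in any of the three models. The limb-side and walking-speed effects are not exposed in this way. The falls total is a descriptive count without a model and lies outside this point.

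The true size is unknown. On the assumed inputs the bias is 0.08 to 0.32 SD. The low end leaves the error rate almost nominal, and the 26.2% figure needs the largest gap, the largest correlation and 30 per group together. If controls were matched on age and sex, the bias would be close to zero. It would be wrong to read this as evidence that the groups are imbalanced or that the results are confounded. The plan should be changed, with medium confidence, because the change is cheap and the amputation effect is central.

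**What to change.** In the Statistical Analysis Plan:

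1. Add age (continuous) and sex as fixed effects to the kinematic, standing-balance and EMG models, besides the terms already named. This presumes that both are among the demographics collected, which the protocol does not specify.
2. Report the model without these covariates alongside, as a sensitivity analysis.
3. If controls were matched, state the matching variables and include them in the models.

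The cost is a few lines of text, about two degrees of freedom and the change in variance tabulated above. The precision loss matters mainly at around 10 per group when age predicts the outcome weakly, and there the unadjusted results would let a reader see the effect of adjusting.

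### For kinematic and standing balance variables the SAP states only main effects and does not define limb side for controls, so both estimates depend on an unstated coding and cannot show which limb differs.

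*Combined protocol and SAP*

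**What the plan says.** The Statistical Analysis Plan names two targets for walking kinematics, one model per speed: "The main effect of amputation and limb side on kinematic variables will be assessed". For standing balance, one model per vision condition, it says "The main effect of amputation and limb side on standing balance variables will be assessed using a linear mixed model analysis". For these outcomes it names no interaction, no comparison of one type of limb with controls, and no comparison of the two limbs within prosthesis users.

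The data are collected limb by limb. On quiet standing the Study Protocol says "This allowed recording of the plantar center of pressure (CoP) under both limbs by each force plate", and its Data Analysis paragraph adds "Plantar CoP of each limb in the coronal plane (elliptical area) were derived". For users it separates the two limbs: "Position of the markers on the prosthetic limb approximated matched those on the contralateral side". Controls have no such labels. The electrode description, which concerns EMG and is only context here, reads "tibialis anterior of the sound limb (or both limbs in case of control subjects". Nowhere do the documents say whether limb side means prosthetic/sound, left/right or dominant/non-dominant, or how a control's two limbs enter the factor.

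**The concern.** In a prosthesis user the two limbs differ in kind: one is a device and the other is intact. The useful questions are whether the prosthetic limb differs from a control limb, whether the sound limb does, and how far the two differ from each other. Two main effects do not answer these separately.

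Controls also have no natural position on a prosthetic/sound factor, so the analyst must choose one. That choice changes what the amputation term and the limb-side term each estimate. Two analysts who both follow the SAP could report different effects of amputation and different asymmetries from the same data.

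**Working it through.** **Inputs.** The targets come from the Statistical Analysis Plan and the limb-level measurement from the Study Protocol. The documents give no sample size, SD, correlation, effect size or split of amputation side, so there is no planned figure to reproduce. Assumed for illustration: one value per limb per subject, SD 1, between-limb correlation ρ = 0.64, n = 20 per group, two-sided 5% tests.

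**What each coding estimates.** Let p and s be the prosthetic and sound shifts from the control mean, w the users' share of the sample, c1 - c2 the mean difference between paired control limbs, and q the fraction of right-sided amputations.

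- Control limbs paired to the two levels, additive model: amputation = (p + s)/2; limb side = w(p - s) + (1 - w)(c1 - c2).
- All control limbs coded as sound: amputation = s; limb side = p - s.
- Left/right: amputation = (p + s)/2; limb side has size w × |2q - 1| × |p - s| if control limbs do not differ.
- Three levels (prosthetic, sound, control): p, s and p - s are each estimated directly.

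Results for p = -0.8, s = 0, w = 0.5, c1 = c2 (mixed-model fits agree):

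| Coding | Amputation | Limb side |
|---|---|---|
| Paired | -0.4 | -0.4 |
| All controls as sound | 0 | -0.8 |
| Left/right, q = 0.5 | -0.4 | 0 |
| Left/right, q = 0.7 | -0.4 | 0.16 in size (0.5 × 0.4 × 0.8) |
| Three-level | -0.8 and 0 (prosthetic and sound vs control) | -0.8 |

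With s = +0.8, paired coding gives amputation 0 and limb side -0.8. Coding all controls as sound gives amputation +0.8.

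The users'-share rule needs c1 = c2. For a one-limb difference of 1 with w = 0.5 and a control difference of ±0.4, limb side is 0.5 × 1 ± 0.5 × 0.4 = 0.70 or 0.30, not 0.50. With c1 = c2, shares of 40%, 50% and 60% recover 0.4, 0.5 and 0.6 of the asymmetry.

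**Power, paired coding, p = -0.8.** The averaged effect has SE = √((1 + ρ)/n) = √(1.64/20) = 0.286. Prosthetic vs control, using both control limbs, has SE = √((1 + (1 + ρ)/2)/n) = √(1.82/20) = 0.302. These two use the noncentral t with 38 df. The limb-side and either-test columns are simulated.

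| Sound shift s | Averaged effect | Amputation test | Limb-side test | At least one (unadjusted) |
|---|---|---|---|---|
| +0.8 | 0.0 | 5% | 99.9% | 99.9% |
| +0.4 | -0.2 | 11% | 97% | 98% |
| 0 | -0.4 | 28% | 76% | 83% |
| -0.4 | -0.6 | 53% | 29% | 67% |
| -0.8 | -0.8 | 78% | 5% | 79% |

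Prosthetic vs control has 73% in every row, or 56% with Bonferroni adjustment for three contrasts. The averaged effect overtakes it once s reaches about -0.72 (against the adjusted contrast, about -0.44).

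**Cost in precision.** The ratio of interval widths, limb-specific to averaged, is √((3 + ρ)/(2(1 + ρ))) = √(3.64/3.28) = 1.05. It is 1.13 at ρ = 0.3 and 1.01 at ρ = 0.9.

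**Variance assumption.** A three-level model with one pooled residual variance has about 95% coverage when all SDs are equal. If the prosthetic-limb SD is 1.5 or 2 times the others (assumed), coverage for prosthetic vs control falls to about 92% or 88-89%. If it is half, coverage for sound vs control is about 92%.

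**The case against.** The strongest reply is that the SAP names limb side as well as amputation, so the two terms must be read together. Under paired coding this largely stands. When only the prosthetic limb differs, the limb-side test has about 76% power, close to the 73% of the direct contrast. When the limbs shift in opposite directions it has 99.9%, beside an amputation effect of zero. A reader might infer that the planned analysis would miss such effects or report no effect of amputation. That would be true of one line of the output, not of the whole. The reply does not carry over to left/right coding, where the limb-side effect can vanish.

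A reader might also infer that a one-limb difference is always halved. It is not: the halving needs one limb of each control at each level, and coding all control limbs as sound removes it.

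Nor does the SAP rule out an interaction or follow-up contrasts. It is a short text that neither plans nor excludes them. An interaction alone would not settle the matter: with left/right coding and an even split of amputation sides it is also about zero.

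Finally, the averaged amputation effect is a legitimate target, and it has more power when both limbs shift alike (78% against 73%). That stands, and it is a reason to keep the averaged effect.

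**Conclusion.** The point holds as a gap in specification with a cheap remedy. The stated targets do not say which limb differs, and the undefined position of controls lets the same data give an amputation estimate of -0.4 or 0 and a limb-side estimate of -0.4, -0.8 or 0 in the one-limb example. Those values follow from algebra once the cell means and equal groups are assumed. Halving of the amputation effect, and scaling of the limb-side effect by the users' share, are conditional on the coding. The scaling also requires that paired control limbs do not differ on average.

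The documents do not support a claim that the plan generally fails to detect limb differences. Every power and coverage figure rests on assumed sample sizes, SDs and correlation, and none should be read as the trial's actual power. The point covers kinematic and standing balance variables measured on each limb. The EMG model has no limb-side factor and is outside it.

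**What to change.** Within each planned speed or vision model for these variables:

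- Code limb as one three-level factor (prosthetic, sound, control). Keep both limbs of each control and include a random subject effect.
- Allow limb-specific residual variances, or use robust standard errors.
- Report prosthetic vs control, sound vs control, and prosthetic vs sound, each with a 95% CI.
- Keep the averaged amputation effect as a contrast of the same model: the mean of prosthetic and sound, minus control.
- State whether the contrasts are adjusted for multiplicity.

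An amputation-by-limb term is an alternative only if limb side means prosthetic/sound and control limbs keep two levels under a prespecified pairing rule. It cannot be estimated if each control is reduced to one averaged value.

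The cost is SAP wording and a re-run on data already collected. More contrasts are reported, and limb-specific intervals are about 5% wider than for the averaged effect under the assumed values. If both limbs shift equally, the limb-specific contrast has slightly less power, but the averaged effect is still available from the same fit.

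### The SAP names only main effects, so the amputation effect averages prosthetic and sound limbs in the kinematic and balance models as worded, and in EMG models if both limbs enter together

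*Combined protocol and SAP*

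**What the plan says.** The Statistical Analysis Plan section describes three sets of mixed models.

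- **Kinematics**, one model per walking speed: "The main effect of amputation and limb side on kinematic variables will be assessed using a linear mixed model analysis".
- **Standing balance**, one model per vision condition: "The main effect of amputation and limb side on standing balance variables will be assessed using a linear mixed model analysis".
- **EMG**: "The main effect of amputation and walking speed on EMG variables will be assessed using a linear mixed model analysis", fitted as a "linear mixed model analysis for each muscle group separately".

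No interaction, limb-specific contrast or random-effects structure is given.

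The Study Protocol section sets out what is recorded. For EMG, three muscles are bilateral in everyone: "rectus femoris of both limbs, medial hamstring of both limbs, and gluteus medius of both limbs". The other two are one-sided in prosthesis users. Tibialis anterior is recorded on "tibialis anterior of the sound limb (or both limbs in case of control subjects"), and medial gastrocnemius is handled the same way.

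In quiet standing each foot has its own force plate: "This allowed recording of the plantar center of pressure (CoP) under both limbs by each force plate". Under Data Analysis, "Plantar CoP of each limb in the coronal plane (elliptical area) were derived". Balance data are therefore limb-specific in both groups.

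Data Analysis also says that iEMG is computed per muscle in four parts of the gait cycle and scaled by each subject's own whole-cycle average. It does not say whether that average is taken within limb, muscle and speed or across them. It does not say how a user's two limbs are combined, selected or separated.

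**The concern.** In a prosthesis user the two limbs may differ from a control limb by different amounts, or in opposite directions. A model with one amputation coefficient cannot show this. It cannot say whether the prosthetic side, the sound side or both differ from controls, and differences of opposite sign cancel.

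Naming limb side in the kinematic and balance models appears to deal with this. It does not, because a side main effect is common to both groups and leaves the amputation coefficient unchanged.

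For EMG the same label can also carry two meanings. The amputation effect may be a limb average for three muscles, but it is a sound-limb contrast for the other two. Comparing amputation effects across muscles would then compare different quantities.

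**Working it through.** The documents give no sample size, alpha, effect size or variance, so there is no planned figure to reproduce. The check is algebra on the named model terms, with assumed effects for illustration.

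**1. What the coefficients estimate.** Let P and S be the prosthetic-side and sound-side differences from controls. Set both control limbs to 0, with equal records per limb. The four cell means are control 0 and 0, users P and S.

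- Amputation coefficient = user mean − control mean = (P + S)/2, with or without a side main effect.
- Side coefficient, with side coded prosthetic/sound and control limbs assigned to sides, equal groups = [(P + 0) − (S + 0)]/2 = (P − S)/2.

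| Assumed P / S (SD) | Amputation effect | Side effect | True P − S |
|---|---|---|---|
| +0.5 / +0.5 | 0.50 | 0 | 0 |
| +0.5 / 0 | 0.25 | 0.25 | 0.5 |
| +0.5 / −0.5 | 0 | 0.50 | 1.0 |

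A least-squares fit to the cell means returns these values. With balanced data they equal the mixed-model expectation. Adding the amputation-by-limb term recovers P and S separately.

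**2. Unequal records per limb.** Walking Data Collection asks for 10 clean foot strikes and gives no split between limbs. If strikes enter individually in a model with a subject intercept and no limb term, the average is weighted by record count. With P = +0.4, S = −0.4 and 5 prosthetic-side against 10 sound-side records, the expected coefficient is (5 × 0.4 − 10 × 0.4)/15 = −0.13, not 0. A simulated mixed model with 300 subjects per group gave −0.11. In standing, each trial yields one record per limb, so a simple average applies when trials are complete.

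**3. Which EMG muscles are affected.** Three of the five are bilateral. If both limbs enter one model per muscle, step 1 applies. If each limb's muscle is modelled separately, it does not. For tibialis anterior and medial gastrocnemius only S exists in users, so the effect is S.

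**4. Normalisation.** If iEMG is divided by its whole-cycle average within limb, muscle and speed, the whole-cycle value averages 1 for everyone and carries no group contrast. If the average is pooled across both limbs, the whole-cycle limb average is fixed and its amputation effect is zero by construction. Prosthetic and sound values must then move in opposite directions.

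**5. Precision of a limb-specific contrast.** With equal groups, one record per limb and limb correlation ρ, the ratio of the SE of prosthetic versus control to the SE of the average is √[(3 + ρ)/(2(1 + ρ))].

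- ρ = 1: √(4/4) = 1.00
- ρ = 0: √(3/2) = 1.22
- ρ = −0.5: √(2.5/1) = 1.58
- ρ = −0.8: √(2.2/0.4) = 2.35

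The SE is 0 to 22% larger when ρ is non-negative, and more when it is negative, which pooled normalisation could produce.

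**6. Power, as illustration only.** Assume EMG variance shares of 0.5 subject, 0.25 limb and 0.25 residual, two limbs × two speeds, 20 per group, and two-sided 5% tests.

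- SE of the average = √(2 × 0.6875/20) = 0.262.
- SE of prosthetic versus control = √((0.875 + 0.6875)/20) = 0.280.
- At +0.5/0, power is 15% for the average against 41% for the prosthetic contrast (30% with Bonferroni over two).
- At +0.5/+0.5 the average does better: 46% against 41% (30%).

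These shares are invented and ignore the normalisation in step 4, so they show direction only.

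**The case against.** **EMG averaging is not established.** A reader might infer that the EMG analysis pools the two limbs. The documents do not support that. Models are fitted separately by muscle group, a term the plan does not define, and electrodes are listed by muscle and limb. Treating each limb's muscle as its own group fits the text and removes the averaging. This stands: what is certain for EMG is an unstated data-entry rule, and the averaging is conditional on it.

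**A main effect does not exclude an interaction.** In so short a plan the authors may have intended one, and the coding of limb side in controls is undefined. It remains true that the words name main effects only, and a model fitted to those words averages the limbs.

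**The limb average is a legitimate target.** It is more powerful when both limbs shift alike. This also stands, so it would be wrong to call the analysis invalid. But the plan does not say that an average is what it wants.

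**There may be a reason to omit side for EMG.** Two muscles have no prosthetic-side record, which could explain one specification without side. The documents do not say so, and separate models allow the terms to differ by muscle.

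**The EMG power figures rest on invented variances for a normalised outcome.** This is correct, and the conclusion does not rely on them. A reader who took the shortfall at +0.5/0 as the trial's expected loss of power would go beyond the documents.

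**Conclusion.** The point holds in this form. Fitted as worded, the kinematic and standing-balance models give one amputation effect averaged over prosthetic and sound limbs. With equal records per limb this is (P + S)/2; otherwise it is weighted. With equal groups, no side difference in controls and side coded prosthetic/sound, their limb-side effect is half the users' prosthetic–sound difference.

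For the three bilateral EMG muscles the same follows only if both limbs enter one model. For the two distal muscles, amputation means sound limb versus control. The distortion ranges from none, when the limbs shift alike, to complete cancellation, when they shift equally in opposite directions.

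It would be wrong to conclude that copying limb side into the EMG model as a main effect would cure this: the amputation coefficient in step 1 does not change.

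This should be corrected. The algebra is firm; confidence is medium because the fitted terms and the entry of EMG limbs are not stated.

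**What to change.** 1. In the kinematic and balance models, and in EMG models for rectus femoris, medial hamstring and gluteus medius, replace the two-level amputation factor with a limb factor (prosthetic, sound, control). Alternatively, add an amputation-by-limb term with a stated rule matching control limbs to sides. Keep walking speed in the EMG models. Include a random effect for subject and, where there are repeated records, for limb within subject.
2. Report prosthetic versus control and sound versus control, with a stated multiplicity approach such as Bonferroni over the two. Report the limb average beside them if it is wanted.
3. State how both limbs' EMG records enter. Label the tibialis anterior and medial gastrocnemius results as sound limb versus control, with a subject random effect for the two control limbs.
4. State whether iEMG normalisation is within limb, muscle and speed or pooled across limbs, and omit any region that it makes degenerate.

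**Cost.** Wording and model terms only. If both limbs would otherwise enter one model per muscle, EMG amputation contrasts for the three muscles rise from 3 × 4 = 12 to 24. They rise from 3 × 3 = 9 to 18 if the whole-cycle region is degenerate. At an assumed 5% per test with no true effects, expected false positives go from 12 × 0.05 = 0.6 to 24 × 0.05 = 1.2, or stay at 24 × 0.025 = 0.6 with Bonferroni over each pair. Some precision is lost against the average when both limbs shift alike, as in step 5 of the working.

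Data collection is described mostly in the past tense, so date the change and label it post hoc if results have been seen.
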